**Table 4-1 Protocol deviation codes and analysis sets**

Category Deviation code	Text description of deviation	Data exclusion
Subjects are excluded from PK analysis in case of these PDs:		
TRT02	Subject was randomized but did not take any dose of study treatment	Exclude subject from PK analysis set Subject will be counted in randomized set, but excluded from safety, PD and PK analysis sets
TRT05	Bad compliance to study treatment	Exclude subject from PD and PK analysis sets
Subjects are excluded from PD analysis in case of these PDs:		
TRT02	Subject was randomized but did not take any dose of study treatment	Exclude subject from PD analysis set Subject will be counted in randomized set, but excluded from safety, PD and PK analysis sets
TRT05	Bad compliance to study treatment	Exclude subject from PD and PK analysis sets
Subjects are excluded from PK and PD analysis in case of these PDs:		
		Exclude subject from PK and PD analysis sets

Category Deviation code	Text description of deviation	Data exclusion
TRT02	Subject was randomized but did not take any dose of study treatment	Subject will be counted in randomized set, but excluded from safety, PD and PK analysis sets
TRT05	Bad compliance to study treatment	Exclude subject from PD and PK analysis sets
Subjects are excluded from Safety analysis in case of these PDs:		Exclude subject from Safety analysis set
TRT02	Subject was randomized but did not take any dose of study treatment	Subject will be counted in randomized set, but excluded from safety, PD and PK analysis sets
Subjects are analyzed according to treatment actually received		
TRT04	Wrong treatment arm medication given to the subject by mistake of pharmacist – not according to treatment randomized.	Subject will be analyzed according to treatment actually received (ie the other trt group than randomized)

If updates to this table are needed, an amendment to the SAP needs to be implemented prior to DBL.

## **5 Statistical methods for Pharmacokinetic (PK) parameters**

### **5.1 Variables**

Conventional PK parameters will not be calculated due to the limited sampling schedule.

### **5.2 Descriptive analyses**

## **6 Statistical methods for Pharmacodynamic (PD) parameters**

### **6.1 Primary objective**

The primary objective is to evaluate the effect of AFQ056 in reducing cocaine use.

#### **6.1.1 Variables**

The primary variable is the proportion of cocaine use days during the treatment period (day 1 to last day of treatment).

For each subject, the proportion of cocaine use days will be calculated by dividing the number of days of cocaine use by the number of days during the treatment period, i.e. 98 days for completers and number of days between Day 1 and day of last dose in case of premature discontinuation of study treatment. For the weekly proportions, the full 7 days of data should be available for a subject. For monthly proportions, at least 7 days of data should be available. It is considered as a continuous variable with a normal distribution. The cocaine consumption will be recorded daily (Yes/No) using the timeline follow-back during the entire study.

The timeline follow-back cocaine is a cocaine assessment method that obtains estimates of daily cocaine intake and has been evaluated with clinical and nonclinical populations. Using a calendar, people provide retrospective estimates of their daily cocaine use over a specified time period that can vary up to 12 months from the interview data.

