8.5.1 Clinical Outcome Assessments (COAs)

Clinical Outcome Assessments such as Patient report Outcome and Observer reported Outcome are specific methods for assessment and recording are specified in the Site Operations Manual, with the [Assessment schedule \(Section 8.1\)](#) detailing when each assessment is to be performed. Safety assessments are specified below; methods for assessment and recording are specified in the Site Operations Manual, with the [Assessment schedule \(Section 8.1\)](#) detailing when each assessment is to be performed.

Patient Reported Outcome includes:

- **The TLFB cocaine:** is a cocaine assessment method that obtains estimates of daily cocaine intake and has been evaluated with clinical and nonclinical populations. Using a calendar, people provide retrospective estimates of their daily cocaine use over a specified time period that can vary up to 12 months from the interview date. Several memory aids can be used to enhance recall (e.g., calendar; key dates serve as anchors for reporting cocaine use). The Cocaine TLFB has been shown to have good psychometric characteristics with a variety of cocaine use groups, and can generate variables that provide a wide range of information about an individual's cocaine use (e.g., pattern, variability, and magnitude of cocaine use). The method is recommended for use when relatively precise estimates of cocaine use are necessary, especially when a complete

picture of cocaine use days (i.e., high- and low-risk days) is needed (evaluating cocaine use pre-posttreatment). Clinically, the TLFB can be used to provide feedback about one's cocaine consumption in an effort to increase a client's motivation to change.

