8.8.3 Positive Reinforcement (PR)

For each study visit patients will receive money compensation for travel expenses. In order to stimulate clinic attendance and to enable optimal monitoring of patients' medication adherence and health (including adverse events), patients will be remunerated for complying with study visits and standard requirements (urine submission, TLFB, medication diary, adverse events, and basic physical examination). In order to reinforce regular participation with study assessments a bonus will be provided each time patients attend two consecutive study visits. Finally, patients will receive additional remuneration for their time investment in case of ECG-evaluations and for extended study visits with additional questionnaires and/or PK-blood sampling. The maximum remuneration for patients complying with all study assessments. Given our experience with pharmacotherapy studies with cocaine dependent patients, we expect that patients, on average, will attend a maximum of 70-80% of all planned study visits.

In addition to positive reinforcement, participants will be stimulated at every planned visit and encouraged for attending appointments, as well as adherence to the protocol.

Positive Reinforcement will be made available for the sites as a separate document.

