11.4.3 Handling of missing values/censoring/discontinuations

In case of premature discontinuation of study treatment, the calculation of the primary variable will be done on the period with both TLFB data available and study treatment was taken. No missing data is expected between visits per the TLFB completion guidelines and investigator's checks at the visits.

For sensitivity analysis, the incomplete profiles will be included in longitudinal analyses.

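### The primary variable's denominator in SAP 6.1.1 and protocol 11.4.1 omits the TLFB-available condition of protocol 11.4.3; read literally, on-treatment days without TLFB act as non-use days

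*SAP*

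**What the plan says.** SAP 6.1.1 obtains the overall proportion by "dividing the number of days of cocaine use by the number of days during the treatment period", and specifies those days as "98 days for completers and number of days between Day 1 and day of last dose in case of premature discontinuation of study treatment". Protocol 11.4.1 gives the same day counts. Neither place makes the count depend on TLFB being available.

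Protocol 11.4.3 has a different rule for early stoppers. It begins "In case of premature discontinuation of study treatment, the calculation of the primary variable will be done" and restricts the calculation to "the period with both TLFB data available and study treatment was taken". The same paragraph adds: "No missing data is expected between visits per the TLFB completion guidelines".

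Three other places bear on this:

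- SAP 6.1.1 sets availability rules for the descriptive summaries. A weekly proportion needs all 7 days and a monthly one at least 7 days, with a month set at 28 days in SAP 6.1.2. The overall proportion, which is the primary variable, gets no such rule.
- Protocol 8.5.1 describes TLFB as retrospective: "people provide retrospective estimates of their daily cocaine use over a specified time period".
- Protocol 8.8.3 says of attendance: "we expect that patients, on average, will attend a maximum of 70-80% of all planned study visits".

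**The concern.** A programmer who follows SAP 6.1.1 as written and one who follows protocol 11.4.3 get different values for the same discontinuer whenever the last TLFB day falls before the last dose. The difference goes one way only: the calendar-time denominator gives the lower, more favourable, figure.

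Such a gap can arise. The expectation of no missing data covers days between visits, not the stretch after the last interview. Under protocol 7.2, absence becomes a discretionary ground for discontinuation only after more than 6 consecutive missed visits, which is about three weeks at two visits a week. The minimum data listed there for collection after stopping are new or concomitant treatments and adverse events; TLFB is not among them. After withdrawal of consent (7.3), later data are treated as missing.

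The direction also differs from the rest of the plan. Unexcused missed urine samples count as positive (study design description, protocol section 3), and patients who do not complete 14 weeks count as not abstinent (SAP 6.2.1).

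**Working it through.** **Inputs from the documents.** T = 98 for completers, or Day 1 to last dose for discontinuers (SAP 6.1.1, protocol 11.4.1). SD 32 percentage points and 30 patients per arm (protocol 11.7). The sample size of 60 cannot be reproduced, because the visible text gives no effect size or decision criterion. Only the standard error is used here.

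**Assumed inputs.** r, the use rate on days with TLFB, and m, the on-treatment days without TLFB. The documents give neither. T counts both the first and the last day.

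**Formulas.**

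- Literal SAP 6.1.1 / protocol 11.4.1: r(T - m)/T = r(1 - m/T)
- Available days only (protocol 11.4.3): r(T - m)/(T - m) = r

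**One discontinuer.** r = 50%, TLFB to Day 25, last dose on Day 32, so T = 32 and m = 7.

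- Literal: 0.5 × 25/32 = 39.1%
- Available days: 50.0%
- Missing days scored as use: (0.5 × 25 + 7)/32 = 19.5/32 = 60.9%

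**One completer.** T = 98, r = 50%.

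| Days without TLFB | Literal | Available days |
|---|---|---|
| 0 | 50.0% | 50.0% |
| 7 | 46.4% | 50.0% |
| 14 | 42.9% | 50.0% |
| 28 | 35.7% | 50.0% |

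Each missing week costs 0.5 × 7/98 = 3.6 points. With m = 0 the rules agree exactly.

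**Between arms.** The SE of a simple difference in means is 32 × √(2/30) = 8.26 points.

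- Equal missingness, true 50% against 30%: the 20-point difference becomes 20 × (1 - m/T), which is 18, 16 or 14 points at 10%, 20% or 30% missing days.
- Unequal missingness, true 50% in both arms: 10 percentage points more missing days on active gives a false benefit of 0.5 × 10 = 5 points, or 5/8.26 = 0.61 SE.
- A milder case: 6 of 30 patients in one arm stop as in the discontinuer example, and no days are missing in the other arm. The arm mean falls by 6 × 10.9/30 = 2.2 points, or 2.2/8.26 = 0.27 SE.

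All missing-day fractions and dropout counts here are illustrations, not predictions.

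**The case against.** A reader might infer more than the documents support in five ways.

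- **That the plan scores missing days as abstinent.** No visible text says so. It is the arithmetic result of applying the formula as written. SAP 6.1.3 (after its first line) to 6.1.3.3 are redacted and may hold a rule for missing days.
- **That the SAP departs from the protocol.** The tension starts inside the protocol, between 11.4.1 and 11.4.3. The SAP carries over the first and does not repeat the second.
- **That 98 days for completers contradicts 11.4.3.** That rule covers early discontinuation only. For completers the visible text simply has no rule for gaps.
- **That 70-80% attendance means 20-30% of days are missing.** TLFB is retrospective, with recall of up to 12 months, so a missed visit can be filled in at the next one attended.
- **That patients miss visits when they are using.** Neither document says this, and the argument does not need it.

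The gap is also likely to be narrow. Protocol 7.2 calls for a visit about one week after the last dose, at which recall could cover the final stretch. Last dose is established from diaries and pill counts, and a contact that supplies these could often supply TLFB too. Protocol 11.4.3 and 11.4.4 already plan longitudinal analyses with incomplete profiles and a look at the missing-data mechanism.

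All of this stands, and it reduces the likely size. It does not reconcile the two denominators. Patients lost to follow-up or withdrawing consent can still have a stretch between last interview and last dose. The SAP's weekly and monthly rules show that it foresees missing days, yet its visible text gives the primary proportion no availability condition.

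**Conclusion.** The point holds as a conflict between stated rules. For discontinuers, SAP 6.1.1 and protocol 11.4.1 give a denominator that does not carry the TLFB-available condition of protocol 11.4.3. For completers, gaps are unaddressed. Followed literally, the formula lowers a patient's proportion by the fraction of treatment days without TLFB.

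The size cannot be stated from the documents. It depends on how many on-treatment days lack TLFB and whether that differs by arm. The most likely source is the interval between last TLFB interview and last dose in patients who drop out or are lost to follow-up. The between-arm figures assume a simple comparison of means, because the Bayesian model is redacted. The point should be corrected because it concerns the primary variable and costs little, not because a large bias has been shown.

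**What to change.** In SAP 6.1.1, define the primary variable for completers and discontinuers alike as days of reported use divided by days with TLFB data, both counted from Day 1 to last dose. Make the same change in protocol 11.4.1 at the next amendment, so that it agrees with 11.4.3.

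Add a table of on-treatment days without TLFB by arm. Add a sensitivity analysis that scores those days as use, unless the redacted SAP text already contains one. It is needed because the available-day denominator assumes that unreported days resemble reported ones.

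The cost is a short SAP amendment before database lock, one table and at most one extra analysis, with no new data. The protocol wording needs a formal amendment under 13.1, which is why it can wait for the next one.

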#### **6.1.2 Descriptive analyses**

The cocaine daily consumption (Yes/No) will be listed by treatment, subject, and day. The overall proportion of cocaine use days, along with the monthly and weekly proportions will be listed by treatment and subject.

A descriptive summary table of the proportion of cocaine use days will be provided by treatment and week. A similar table shall also be provided to summarize the proportion of cocaine use days by treatment and month (28 days was selected as a nominal length month, rather than actual calendar month). The overall proportion of cocaine use days will also be summarized.

#### **6.1.3 Statistical model, assumptions and hypotheses**

A Bayesian analysis will be conducted on the proportion of cocaine use days

Commercially Confidential Information

**6.1.3.1 Model checking procedures**

Commercially Confidential Information

**6.1.3.2 Sensitivity analyses**

Commercially Confidential Information

**6.1.3.3 Supportive analyses**

Commercially Confidential Information

#### 6.1.3.4 Graphical presentation of results

Commercially Confidential Information

### 6.2 Secondary objectives

The secondary objectives are to assess the effect of AFQ056 on other measures of cocaine use and on measures of alcohol use, to assess the safety and tolerability and to evaluate the pharmacokinetics of AFQ056.

#### 6.2.1 Variables

Two urine samples per week will provide a quantitative measure of cocaine's metabolite Benzoylecgonine.

Alcohol consumption will be recorded by the subjects using timeline follow-back. The number of drinks will be recorded daily. For the weekly consumption, the full 7 days of data should be available for a subject. For monthly consumptions, the full 28 days of data should be available.

The timeline follow-back alcohol is a drinking assessment method that obtains estimates of daily drinking and has been evaluated with clinical and nonclinical populations. Using a calendar, people provide retrospective estimates of their daily drinking over a specified time period that can vary up to 12 months from the interview data.

Abstinence last x weeks at end of treatment

Binary response variables based on abstinence will be calculated as follows:

A subject is considered abstinent the last x weeks of treatment if they completed the 14 weeks treatment period and were abstinent the last x weeks (with  $x=1, 2, 3, \dots, 14$ ).

If a subject didn't complete 14 weeks they will be considered as not abstinent.

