7.1 Study completion and post-study treatment

Each subject will be required to complete the study in its entirety and thereafter no further study treatment will be made available to them.

Study completion is defined as when the last subject completes their Study Completion visit, and any repeat assessments associated with this visit have been documented and followed-up appropriately by the Investigator, or in the event of an early study termination decision, the date of that decision.

All randomized and/or treated subjects will have a safety follow-up call conducted 14 days after last administration of study treatment. The information collected is kept as source documentation. All SAEs reported during this time period must be reported as described in [Section 9.2](#) and the Site Operations Manual. Documentation of attempts to contact the subject should be recorded in the source documentation.

Continuing care should be provided by investigator and/or referring physician based on subject availability for follow-up. This care may include:

- promote compliance for the visits schedule for urine samples collection
- promote compliance for data entry in TLFB cocaine , as well as TLFB alcohol

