11.5.1.2 Measures of alcohol use

Alcohol consumption will be recorded by the patients using TLFB. The number of standard drinks will be recorded daily.

The proportion of days of alcohol consumption during the study treatment period will be compared between groups using an ANCOVA model with treatment as factor and past alcohol consumption as covariate.

The longitudinal profiles (daily number of drinks, weekly and monthly mean number of drinks) will be explored.

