### **1.4 Study design and treatment**

This is a randomized, subject and investigator blinded, parallel group, placebo-controlled study in approximately 60 patients with cocaine use disorder. The study consists of: about 17-day screening period followed by a 12-day baseline; a 98-day out-patient treatment period (14-day up-titration dose regimen followed by 84-day maintenance dose) and finally an end of study visit evaluation approximately 14-days after the last study drug administration. The total

duration for each patient in the study is up to approximately 20-weeks including screening and baseline. The study design is summarized in Figure 1.4-1 below.

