#### 6.2.2 Descriptive analyses

The log-transformed quantitative urine measurements of Benzoylecgonine will be summarized by treatment and visit / time and weekly. To obtain the weekly profiles, the BE measurements obtained by a subject during each week (aligned with the weekly profiles of TLFB) will be averaged. These data shall also be listed by subject, and time point.

Descriptive summary tables shall be provided to summarize the alcohol consumption by treatment and week, and by treatment and month. The alcohol daily consumption, weekly consumption and monthly consumption will be listed by subject and time point. If country is a significant effect in the model stated in section 6.2.3 then summary statistics will also be provided by country.

The amount spent on cocaine will be summarized by treatment and listed by subject and time point. The amount spent will be converted in Euros for the summary statistics, using the exchange rates recorded on 7th August 2019 from XE currency converter website (<https://www.xe.com/currencyconverter/convert>). The exchange rates are:

US Dollar to Euro – 0.891

Swiss Franc to Euro – 0.916

Argentine Peso to Euro – 0.019

The number and % of subjects abstinent the last x weeks will be described both on the PD analysis set and FAS.

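### Does the 28-of-28-day rule for monthly alcohol, without stated month boundaries, need changing when treatment lasts 98 days?

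*SAP*

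**What the plan says.** SAP 6.2.1 sets the completeness rule for monthly alcohol: "For monthly consumptions, the full 28 days of data should be available". The weekly alcohol rule in the same section asks for all 7 days. SAP 6.2.2 uses these values descriptively: "Descriptive summary tables shall be provided to summarize the alcohol consumption by treatment and week, and by treatment and month". It also lists daily, weekly and monthly consumption by subject.

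For cocaine, SAP 6.1.1 again asks for all 7 days of a week, but for months it says "For monthly proportions, at least 7 days of data should be available". It defines the primary variable "during the treatment period (day 1 to last day of treatment"). SAP 6.1.2 gives the length of a month: "28 days was selected as a nominal length month". SAP 1.4 describes a "98-day out-patient treatment period (14-day up-titration dose regimen followed by 84-day maintenance dose").

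Protocol 11.5.1.2 compares the proportion of drinking days over the treatment period by ANCOVA. It then adds: "The longitudinal profiles (daily number of drinks, weekly and monthly mean number of drinks) will be explored". Protocol 7.1 asks sites, in continuing care, to "promote compliance for data entry in TLFB cocaine , as well as TLFB alcohol", and the schedule in Protocol 8.1 carries alcohol self-report into follow-up.

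**The concern.** Three things look wrong together. The month length does not divide the treatment period, so a strict 28-of-28 rule cannot cover all treatment days with whole months. The visible alcohol text gives neither a start day nor an end day, and alcohol self-report continues after the last dose, so the treatment period is not the only conceivable window. And the two substances have the same weekly rule but very different monthly rules, with no visible reason.

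If two programmers chose different windows, the last month of the alcohol table could differ between them. If months run from Day 1 over treatment days only, the end of treatment drops out of the monthly alcohol table but stays in the monthly cocaine table. The two tables would then cover different days and, for early stoppers, different patients. Alcohol use is a stated secondary objective, so its tables should be reproducible.

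**Working it through.** **Inputs.** Treatment days: 7 + 7 + 84 = 98, which reproduces the stated length (SAP 1.4). Month: 28 days (SAP 6.1.2). Minimum data per month: 28 days for alcohol (SAP 6.2.1), 7 days for cocaine (SAP 6.1.1). Weeks: 7 of 7 days for both.

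**Whole periods.** 98/7 = 14 full weeks. 98/28 = 3.5 months, so 98 - 3 × 28 = 14 days remain.

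**Completer, months from Day 1, treatment days only.**

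| Block | Days available | Monthly alcohol (28) | Monthly cocaine (7) |
|---|---|---|---|
| Days 1-28 | 28 | yes | yes |
| Days 29-56 | 28 | yes | yes |
| Days 57-84 | 28 | yes | yes |
| Days 85-98 | 14 | no | yes |

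The days left out are 14/98 = 14.3%. Week 13 is Days 85-91 and week 14 is Days 92-98, so both are complete and the weekly alcohol table shows every one of these days.

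**Early stopper, same blocks, data ending on the stop day (1 to 97).** The alcohol month loses nothing only for a stop on Day 28, 56 or 84, so some days are lost for 97 - 3 = 94 stop days. The largest loss is 27 days (stop on Day 27, 55 or 83). Under the cocaine rule, days are lost only when the last block holds 1 to 6 days: 4 blocks × 6 = 24 stop days, with at most 6 days lost. The weekly alcohol table also loses at most 6 days. A stop on Day 27, for example, leaves weeks 1-3 (Days 1-21) complete and drops only Days 22-27. These counts are of possible stop days, not patients; the documents give no timing of drop-out.

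**Are the two monthly rules in conflict?** The cocaine value is a proportion of days, which part of a month can estimate. The alcohol value is a consumption built from a daily number of drinks. If it is a total, 14 days would give about half of a 28-day figure at the same drinking rate, so a full month is needed for comparability. The 28-of-28 rule is the same principle as the 7-of-7 weekly rule used for both substances. The 7-day cocaine month is the exception.

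**Which window does the text support?** The secondary objective concerns 98 days of administration. Protocol 11.5.1.2 ties the alcohol proportion to the treatment period, and the only window stated for the self-report data is Day 1 to the last day of treatment. SAP 6.2.2 also aligns the weekly urine averages with the weekly self-report profiles, which implies one common time grid. Nothing in either document starts a month on Day 15 or joins Days 85-98 to follow-up days.

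**The case for a change.** The best case for a change is that the boundaries belong in the variable definition or the table description. Both are visible, and neither gives them. Self-report does run into follow-up, so a month reaching past Day 98 is possible in principle. Starting on Day 15 would give three full maintenance months (Days 15-42, 43-70, 71-98) and might even be intended. The protocol also speaks of a monthly mean number of drinks, and a mean per day does not need all 28 days. Stating boundaries and using the 7-day minimum would cost only wording and light programming.

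Part of this stands: the start and end days are unstated, and the SAP does not say whether the monthly value is a total or a mean. The rest is weaker. The alternative windows are possible constructions that no text adopts. The protocol's phrase can equally mean a group mean of each patient's monthly consumption, which does not conflict with the SAP. The 7-day minimum is a trade-off rather than a correction. It would turn a consumption into a mean per observed day, place a 14-day block beside 28-day months, and admit values resting on 7 days. The alcohol model and graphics sections of the SAP are blacked out and may state the boundaries, so it cannot be shown that programmers would in fact diverge.

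**Conclusion.** The observation is accurate but no change to the plan is needed. The gap is an unstated month boundary that an analyst would fill as Day 1 onward over treatment days, in 28-day blocks. That reading leaves 14 of 98 treatment days (14.3%) and an early stopper's last partial month out of one coarse descriptive table and its listing. For completers, the same days appear in full as weeks 13 and 14. For early stoppers, the weekly table omits at most 6 treatment days. The daily listing holds all recorded days, and the treatment-period ANCOVA in Protocol 11.5.1.2 is not subject to the monthly rule. The primary cocaine variable is untouched. No conclusion of the trial turns on the monthly alcohol table.

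This rests on three assumptions: months start on Day 1, only treatment days count, and self-report is complete up to the last dose. Stating the boundary when the tables are programmed would be good housekeeping.
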